9.1.5 Week 14 (Day 99 \pm 7 Days) / Post Operation Follow-up

The following procedures will be conducted at this visit:

1. The Principal Investigator will do a clinical evaluation of the surgical site(s) to confirm adequate healing.

9.2 Evaluation of Efficacy

Clinical Descriptions of Basal Cell Carcinoma

Nodular basal cell carcinoma

A pearly, waxy, semi-translucent nodule sometimes forming a central depression that may or not be ulcerated or crusted. There can be overlying telangiectasias and characteristically there is a "rolled border".

Superficial basal cell carcinoma

An erythematous scaly thin plaque or patch often with areas of hypopigmentation and superficial scarring, occasionally with a thin crust. Careful examination will often show a subtle raised border.

Infiltrative basal cell carcinoma

An erythematous, frequently ulcerated or crusted ill-defined plaque. Occasionally it can be quite indurated or elevated.

Morpheic or sclerosing basal cell carcinoma

An ill-defined hypopigmented sclerotic plaque, sometimes with subtle telangiectasias. Rarely ulcerated or crusted. They can present with an atrophic or depressed appearance centrally often mimicking an old scar.

Micronodular basal cell carcinoma

A dome-shaped sclerotic hypopigmented or flesh colored nodule or plaque with undermining borders where a mass-like effect is palpable below normal appearing skin.

Pigmented basal cell carcinoma

Each of the classic variants described above may be pigmented, particularly in Types III-V skin. These will have blue, black, brown pigmentation usually involving part or most of the tumor with more classic or characteristic features often noted elsewhere.

9.2.1 Assessment of BCCs

One or two treatment-targeted BCCs on each subject will be identified by the Investigator at the following visits: Screening, Baseline, Weeks 2, 6, 8, 10, and 12. The BCCs being followed will be circled in ink, photographed, measured the greatest diameter, and recorded on a body diagram. Circling with ink will only be performed at Baseline, Week 6 and Week 12.

9.2.2 Messenger RNA (mRNA)

Biopsies of treatment targeted tumors done at Baseline as well as excisional samples from the end of study excisions will be evaluated for GLI1 mRNA levels.

9.2.3 Investigator Static Global Tumor Assessment

The Investigator will assess and record the Investigator Static Global Tumor Assessment (ISGTA) of baseline treatment targeted BCC(s) at Baseline, Weeks 2, 6, 8, 10 and Week 12.

Table 4: Investigator Static Global Tumor Assessment

0	Clear - no evidence of residual tumor is seen or palpated, faint ill-defined macular erythema may be present; normal skin markings are seen
1	Almost clear - residual macular erythema is clearly seen but there is no palpable* obvious tumor, scale, erosions, or ulcerations; normal skin markings are seen
2	Minimal residual tumor - macular erythema is clearly seen and visible slight palpable tumor with or without scale, erosions, ulcerations may be present; normal skin markings are not clearly visible
3	Clearly visible tumor - is seen and felt on palpation with or without rolled borders erosion, ulceration, or scale; normal skin markings not seen

^{*}Only evaluated at visits conducted at the study center.

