9. STUDY PROCEDURES AND EVALUATIONS

The study will be conducted as outlined in the Schedule of Assessments (Table 1). The Screening, Week 6, Week 12 and Week 14 study visits will take place in person. The Weeks 2, 8, and 10 visits may take place using telemedicine and/or an in-person visit. Telemedicine will be conducted using a 21 CFR Part 11 and HITRUST/HIPAA compliant platform on a mobile device. Telemedicine video and phone conferences are not recorded.

All subject information and data obtained during the study visits will be recorded in the electronic source documents, applicable study logs, and eCRFs.

Investigators must have appropriate, documented experience and training, or obtain approval from PellePharm based on experience (or through additional training organized by PellePharm).

At each study visit, every attempt should be made to ensure that the same Investigator assesses the same subject. The sponsor realizes that the conduct of a clinical trial involves a team of study staff who perform a variety of functions under the supervision of the Principal Investigator. Tasks and responsibilities are delegated by the Principal Investigator as dictated by local laws and institutional regulations. There are specific tasks that PellePharm requires be done by a licensed healthcare professional with appropriate experience. As outlined below and in the Schedule of Assessments (Table 1), these tasks include biopsy for biomarkers, measuring and mapping of treatment-targeted tumor(s), determination of clinical tumor type, recording application site reactions, and the determination of the ISGTA.

PellePharm also realizes that scheduling visits can be challenging and has allowed for study windows. It should be noted that the indicated visit day is in reference to the Baseline visit. For example the Week 6 (Day 43) visit is intended to be Day 43 after the Baseline visit.

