6.7.3 Exploratory Efficacy Analysis

The exploratory endpoint of investigator static global tumor assessment (ISGTA) will be summarized by visit on a by tumor level. Proportion with success as defined by Clear/Almost Clear will be provided. Results will be analyzed with a Cochran-Mantel-Haenszel (CMH) test.

Tumor area will be evaluated with an analysis of covariance (ANCOVA) with treatment group as factor and baseline value as covariate. Analysis is on a by tumor level. Pairwise comparisons as well as any treated (combining all patidegib groups) versus vehicle will be performed using contrasts within the ANCOVA.

The proportion of baseline treated tumors are smaller at each study visit based on photographic review will be summarized by treatment group. Results will be analyzed between groups and all treated (combining all patidegib groups) versus vehicle with a CMH test. Tumor area will be summarized by visit.

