	XX XX (XX.X%)	XX XX XX (XX.X%) XX (XX.X%) XX (XX.X%) XX (XX.X%)	XX XX XX XX (XX.X%) XX (XX.X%) XX (XX.X%) XX (XX.X%) XX (XX.X%) XX (XX.X%) XX (XX.X%) XX (XX.X%) XX (XX.X%) XX (XX.X%) XX (XX.X%) XX (XX.X%) XX (XX.X%) XX (XX.X%) XX (XX.X%) XX (XX.X%) XX (XX.X%) XX (XX.X%) XX (XX.X%) XX (XX.X%) XX (XX.X%) XX (XX.X%) XX (XX.X%) XX (XX.X%) XX (XX.X%) XX (XX.X%) XX (XX.X%) XX (XX.X%) XX (XX.X%) XX (XX.X%) XX (XX.X%) XX (XX.X%) XX (XX.X%) XX (XX.X%) XX (XX.X%) XX (XX.X%) XX (XX.X%) XX (XX.X%) XX (XX.X%) XX (XX.X%) XX (XX.X%) XX (XX.X%)	XX XX XX XX XX (XX.X%) XX (XX.X%) XX (XX.X%) XX (XX.X%) XX (XX.X%) XX (XX.X%) XX (XX.X%) XX (XX.X%) XX (XX.X%) XX (XX.X%) XX (XX.X%) XX (XX.X%) XX (XX.X%) XX (XX.X%) XX (XX.X%) XX (XX.X%) XX (XX.X%) XX (XX.X%) XX (XX.X%) XX (XX.X%) XX (XX.X%) XX (XX.X%) XX (XX.X%) XX (XX.X%) XX (XX.X%) XX (XX.X%) XX (XX.X%) XX (XX.X%) XX (XX.X%) XX (XX.X%) XX (XX.X%) XX (XX.X%) XX (XX.X%) XX (XX.X%) XX (XX.X%) XX (XX.X%) XX (XX.X%) XX (XX.X%) XX (XX.X%) XX (XX.X%) XX (XX.X%) XX (XX.X%) XX (XX.X%) XX (XX.X%) XX (XX.X%) XX (XX.X%) XX (XX.X%) XX (XX.X%) XX (XX.X%) XX (XX.X%) XX (XX.X%) XX (XX.X%) XX (XX.X%) XX (XX.X%) XX (XX.X%) XX (XX.X%) XX (XX.X%) XX (

Repeat for Weeks 6, 8, 10, 12

Note: Missing values imputed using LOCF.

SOURCE: USERNAME\SPONSOR\PROJECT\JOBNAME (DATE,TIME)

^a Success is defined as Clear or Almost clear.

^b P-value from Cochran-Mantel-Haenszel (CMH) test.

Table 14.2.3.2: Analysis of the Exploratory Efficacy Endpoint: ISGTA at Weeks 2, 6, 8, 10 and 12 (Per Protocol Population)

As Table 14.2.3.1 for Per Protocol

Table 14.2.4.1: Analysis of the Exploratory Efficacy Endpoint: Area of Baseline Treated Tumors based on Photographic Review (Intent-to-Treat Population)

	Patidegib Gel 2% QD (N=xx)	Patidegib Gel 2% BID (N=xx)	Patidegib Gel 4% QD (N=xx)	Patidegib Gel 4% BID (N=xx)	Vehicle Gel (N=xx)
Baseline					
Number of tumors	XX	XX	XX	XX	XX
Mean	XX.X	XX.X	XX.X	XX.X	XX.X
SD	XX.XX	XX.XX	XX.XX	XX.XX	XX.XX
Median	XX.X	XX.X	XX.X	XX.X	XX.X
Min. to Max.	xx to xx	xx to xx	xx to xx	xx to xx	xx to xx
Mid-Study					
Number of tumors	XX	XX	XX	XX	XX
Mean	XX.X	XX.X	XX.X	XX.X	XX.X
SD	XX.XX	XX.XX	XX.XX	XX.XX	XX.XX
Median	XX.X	XX.X	XX.X	XX.X	XX.X
Min. to Max.	xx to xx	xx to xx	xx to xx	xx to xx	xx to xx
Percent Change from Baseline ^a					
Number of tumors	XX	XX	XX	XX	XX
Mean	XX.X	XX.X	XX.X	XX.X	XX.X
SD	XX.XX	XX.XX	XX.XX	XX.XX	XX.XX
Median	XX.X	XX.X	XX.X	XX.X	XX.X
Min. to Max.	xx to xx	xx to xx	xx to xx	xx to xx	xx to xx

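### ISGTA success can be graded without palpation at telemedicine visits, and the SAP neither separates those grades nor stops LOCF from carrying them into Week 12

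*Protocol*

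**What the plan says.** **The scale.** Protocol 9.2.3 (Table 4) defines grade 1, almost clear, partly by the condition that "there is no palpable* obvious tumor, scale, erosions, or ulcerations". The asterisk leads to the footnote "Only evaluated at visits conducted at the study center". Grade 0, clear, also refers to touch ("no evidence of residual tumor is seen or palpated") but has no asterisk.

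**The visits.** ISGTA is scored for "baseline treatment targeted BCC(s) at Baseline, Weeks 2, 6, 8, 10 and Week 12". Protocol section 9 fixes some visits as in person: "The Screening, Week 6, Week 12 and Week 14 study visits will take place in person". For the others it says: "The Weeks 2, 8, and 10 visits may take place using telemedicine and/or an in-person visit".

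**The analysis.** SAP 6.7.3 gives one definition of success for all visits: "Proportion with success as defined by Clear/Almost Clear will be provided". It tests success with a Cochran-Mantel-Haenszel (CMH) test. SAP Table 14.2.3.1 repeats that test at Weeks 2, 6, 8, 10 and 12. SAP 6.1 applies LOCF to missing exploratory efficacy data, and the table shell repeats this: "Note: Missing values imputed using LOCF". SAP 6.1 also promises analyses without imputation, but the two ISGTA shells (14.2.3.1 for ITT, 14.2.3.2 for per protocol) carry only the LOCF note.

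**The concern.** Palpation is part of what makes a lesion almost clear, and almost clear counts as success. A visit held by video cannot include it. The plan does not say how to grade when palpation was not done, and it does not separate remote from in-person grades. The planned ISGTA listing (16.2.6.1) has no column for visit mode.

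Two consequences follow. First, at Weeks 2, 8 and 10 some subjects may be graded on one criterion and some on another, and the outputs would not show which. Second, LOCF can put a grade given without palpation into Week 12, a visit that is meant to be in person. Since an exploratory objective is to judge how useful ISGTA is, a time course that partly reflects visit mode would weaken that judgement.

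**Working it through.** The documents give no figure for this endpoint: no expected success rate, no power and no count of remote visits. The check is therefore one of logic, with arithmetic only for scale.

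**1. Direction of the change in criterion.** Let V mean that the lesion meets the visual conditions for grade 0 or 1, and let P mean that tumor can be felt. I read the footnote as dropping the palpation condition at a remote visit, with the visual features judged in the same way.

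- Success in person = V and not P.
- Success at a remote visit = V.
- Difference = the share of tumors with V and P; call it q.

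Since q cannot be negative, the remote criterion gives the same success rate or a higher one for the same lesions, never a lower one.

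**2. Which lesions are affected.** Table 4 also separates grades 1 and 2 by sight. Grade 1 has normal skin markings and no scale, erosions or ulcerations. Grade 2 has a visible tumor and skin markings that are not clearly visible. A lesion that plainly shows the grade 2 features can be graded 2 on video. Only lesions without those signs, but with tumor that can be felt, contribute to q.

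**3. Effect on the comparison of drug (D) with vehicle (C).** If all grades at a visit are remote, the observed difference is

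(p_D + q_D) − (p_C + q_C) = (p_D − p_C) + (q_D − q_C).

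Equal q leaves the difference in proportions unchanged. It widens if q_D is larger and narrows if q_C is larger. The documents give neither.

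**4. Size of one misgraded tumor.** SAP 4.1 gives 6 active and 3 vehicle subjects per cohort, with four cohorts and one or two tumors per subject. SAP 6.1 pools vehicle.

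| Group | Subjects | Tumors | Shift per tumor (100 / tumors) |
|---|---|---|---|
| One active arm | 6 | 6 to 12 | 16.7 to 8.3 points |
| Pooled vehicle | 4 × 3 = 12 | 12 to 24 | 8.3 to 4.2 points |

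**5. Route into Week 12 through LOCF.** Early-termination grades are mapped by the windows in SAP 6.1.3, and a grade that falls in no window is not analysed. The windows are Days 13–17, 40–46, 54–60, 68–74 and 82–88. If the preceding scheduled visit has a grade, the gaps work as follows.

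| Early-termination day | Grade carried forward | Could it be remote? |
|---|---|---|
| 18–39 | Week 2 | Yes |
| 47–53 | Week 6 | No |
| 61–67 | Week 8 | Yes |
| 75–81 | Week 10 | Yes |

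The early-termination visit follows the Week 12 procedures, which include excision. A subject who stops on Day 78 would therefore have that visit's grade set aside, and a Week 10 grade, possibly given without palpation, would be carried to Week 12. By the same rule, a missing Week 6 grade can be filled from a remote Week 2 grade.

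**6. Illustration for Week 12, on assumed inputs only.** If q is 10% to 30%, and 10% to 20% of Week 12 grades are carried from visits that were all remote, Week 12 success rises by q × share carried: 0.10 × 0.10 = 1 point to 0.30 × 0.20 = 6 points. None of these inputs is in the documents.

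**The case against.** The strongest reply has four parts.

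- **Telemedicine is optional at Weeks 2, 8 and 10.** This stands. A reader might infer that these visits use the easier criterion throughout. The documents support that only for visits actually held remotely, and they do not say how many there will be.
- **Grades 1 and 2 also differ visually.** This stands. A reader might infer that grade 2 tumors are systematically relabelled as successes. Table 4 does not support that. A lesion with normal markings and no visible tumor, found only by touch, fits neither grade as written. In-person grading of it is itself uncertain, so q is an upper bound on the inflation.
- **No direction of bias between arms can be claimed.** This stands. It is tempting to say that extra successes in all arms shrink the drug-vehicle gap, but step 3 shows that this needs unequal q. Flat residual lesions could be more common where tumors shrink, which would widen the gap. Nor can a rise of 10 to 30 points at remote visits be claimed: it only restates an assumed q.
- **The plan already limits the damage.** This stands in part. Results are shown visit by visit, and Weeks 6 and 12 are in person. Early terminators are asked to complete the Week 12 assessments. The per-protocol set excludes most subjects who missed Week 12, although it keeps those who stopped for a related adverse event or documented lack of effect. An as-observed analysis is promised. However, the ITT table uses LOCF, the windows set some early-termination grades aside, and no as-observed ISGTA table is planned.

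**Conclusion.** The point holds in limited form. At visits held remotely, ISGTA success lacks a condition applied in person. It can be easier but not stricter, and it may differ between subjects at the same visit. LOCF can carry such a grade into Week 12, or from Week 2 into Week 6.

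The size cannot be derived from the documents. What can be said is that the arms are small enough for a single misgraded tumor to move an active arm by 8.3 to 16.7 points. The conclusion rests on two conditions: some of the Week 2, 8 and 10 visits are in fact remote, and some lesions lack clear visual signs of grade 2 yet can be felt.

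ISGTA is exploratory and the SAP calls its p-values descriptive. The GLI1 and diameter results are not affected by this point. It is a cheap improvement, not a flaw in the trial's main result.

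**What to change.** Change SAP 6.7.3, Table 14.2.3.1 and its per-protocol counterpart:

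1. Flag each ISGTA grade as in person or remote, and show the flag in Listing 16.2.6.1.
2. Run the CMH success analysis on in-person grades at whatever visit they occur. This always includes Weeks 6 and 12, and it keeps any in-person grades from Weeks 2, 8 and 10.
3. Summarise remote grades separately, without a success test.
4. Allow LOCF into Week 6 or Week 12 only from an in-person grade. Where no earlier in-person on-therapy grade exists, leave the value missing.
5. Add the as-observed ISGTA table that SAP 6.1 promises.

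**Cost.** There will be fewer ISGTA p-values at Weeks 2, 8 and 10, or none. Some carried values will be older: a missing Week 12 grade would come from Week 6 if Weeks 8 and 10 were both remote. The documents do not say whether the eCRF records visit mode; if it does not, that item must be captured. Subjects face no new procedure.

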9.3 Evaluation of Safety

9.3.1 Dermal Safety and Tolerability

Safety and tolerability will be evaluated through assessments of selected local signs and symptoms (pain / burning, pruritus, erythema, edema, and scabbing / crusting). Each of the

identified BCCs will be evaluated separately for these signs and symptoms of application site reactions. Any local skin reaction that requires use of a concomitant therapy or is a cause for study drug interruption or discontinuation should be reported as an AE. The scales to be used for assessing local skin reactions follow:

Table 5: Dermal Safety and Tolerability Scales

Score	Grade	Description
experie	_	eported by the subject as being the greatest intensity they have application site within the last 24 hours at Baseline or since the last visits.
0	None	No pain/burning
1	Mild	Slight burning/stinging sensation; not really bothersome
2	Moderate	Definite warm, burning/stinging that is somewhat bothersome
3	Severe	Hot burning/stinging sensation that causes definite discomfort and may interrupt daily activities and/or sleep
at the a	-	ed by the subject as being the greatest intensity they have experienced ite within the last 24 hours at Baseline or since the last visit at
0	None	No pruritus
1	Mild	Slight pruritus, not really bothersome
2	Moderate	Definite pruritus that is somewhat bothersome
3	Severe	Intense pruritus that may interrupt daily activities and/or sleep
Erythema: as assessed by the Investigator at each site		
0	None	No erythema present
1	Mild	Slight pink coloration
2	Moderate	Definite redness
3	Severe	Marked erythema, bright red to dusky dark red in color
Edema: as assessed by the Investigator at each site		
0	None	No edema
1	Mild	Slight, but definite edema
2	Moderate	Definite edema
3	Severe	Marked edema
Scabbin	ng/Crusting.	as assessed by the Investigator at each site

0	None	No scabbing/crusting
1	Mild	Slight, but definite scabbing/crusting
2	Moderate	Definite scabbing/crusting
3	Severe	Marked scabbing/crusting

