Approximately 36 subjects who meet the study entry criteria will be enrolled into one of four sequential cohorts. As soon as one cohort has been completely enrolled, the next cohort will be enrolled. Each subject will treat no more than two previously untreated biopsy confirmed treatment-targeted nodular BCCs. If the subject has additional non-treatment targeted BCCs they can be treated surgically or with topical agents prior to or during the trial. Within each cohort subjects will be randomized in a 2:1 ratio to receive active or vehicle gel. The sequential cohorts will be:

- Cohort 1: patidegib gel 2% or vehicle, once daily
- Cohort 2: patidegib gel 4% or vehicle, once daily
- Cohort 3: patidegib gel 2% or vehicle, twice daily
- Cohort 4: patidegib gel 4% or vehicle, twice daily

The study drug will be applied topically to the treatment-targeted BCCs and a rim or adjacent skin for 12 weeks.

Information on reported and observed adverse events (AEs) will be obtained at each visit. An abbreviated physical examination (PE) will be performed at Baseline and Week 12.

The treatment-targeted BCCs will be identified by the Investigator at the Baseline visit and will be circled in ink at Baseline, Weeks 6 and 12, and photographed, and measured at all study visits (Baseline, Weeks 2, 6, 8, 10, and 12).

Blood samples for complete blood count and serum chemistry and urine for urinalysis will be collected from subjects at Screening, Week 6, and Week 12.

Subjects who terminate study participation early will be asked to complete all Week 12 assessments, as appropriate, prior to commencement of any alternative therapy for BCCs (if possible). Subjects who discontinue from the study during the treatment period will not be replaced.

If signs or symptoms develop in the treatment areas during the treatment period that restrict daily activities or make continued application of the study drug difficult due to discomfort, the Investigator may instruct the subject to interrupt use of the study drug temporarily and to resume application of the study drug once the signs and symptoms have resolved adequately to the point that the Investigator believes that treatment can safely be resumed. The

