Measure and Map BCCs	X	X	X	X	X	X	X	
Determine Clinical Tumor Type	X							
2mm Punch or Shave Biopsy	X							
End of Treatment Excision							Xh	
BCC Imaging ^I	X	X	X	X	X	X	X	

PellePharm, Inc.

Dose Escalating in Sporadic Basal Cell Carcinomas

Systemic Symptoms		X	X	X	X	X	X	
Patidegib /Vehicle Applications ^J		X	X	X	X	X		
Study drug review/Instructions Dispensation ^J		X	Х	х	х	Х		
Concomitant Medications	X	X	X	X	X	X	X	
Adverse Events	X	X	X	X	X	Х	X	
Review Test Article Compliance/Accountability		X	х	Х	Х	Х	Х	
Clinical Evaluation of Surgical Site(s)								X

BCC= basal cell carcinoma; ET = early termination; ISGTA = investigator static global tumor assessment;

- a for subjects who discontinue early during the treatment period, all procedures outlined for the ET visit should be completed at the time of discontinuation.
- b Must be signed prior to any study procedures.
- ^c Medical history will be updated at Baseline visit.
- d Height will be measured at Baseline only.
- ^e Blood samples for laboratory tests will be collected at Screening. Clinically significant laboratory findings at Week 6 or Week 12 will be repeated at the discretion of the Investigator, and the subject will be followed until resolution (return to normal or to the baseline state) or until clinically stable as determined by the Investigator.
- f Week 6 and 12 serums to be done only for women of child bearing potential
- 8 Only to be done for women of child bearing potential
- h Must be within 48 hours of the Week 12 visit.
- ¹ Imaging requirements are provided in the imaging manual.
- Jubjects will be trained on how to administer the study drug at the Baseline visit and retrained at subsequent visits, if necessary. The study drug may be applied at the study visit. Subjects will record any missed doses and provide to the study site for review

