- 12. Record any AEs reported spontaneously by the subject.
- 13. If the subject is a woman of childbearing potential, the Study Coordinator or designee will provide the subject with three home pregnancy urine tests.
- 14. Schedule the next study visit at Week 2 (Day 15 ± 2 days).

9.1.3 Weeks 2, 6, 8, and 10

The following procedures will be conducted at this visit:

- 1. Record changes in any concomitant medications since the previous visit in the eCRF. Check for prior and concomitant therapies as per Section 7.4.
- 2. Record any new AEs reported spontaneously by the subject or changes in any ongoing AEs.
- 3. The treatment-targeted BCCs identified by the Investigator at the Baseline visit will be photographed and measured using the provided hand held device. *For the Week 6 visit*

- *only*, the treatment-targeted tumors will be, circled in ink, photographed, measured, and recorded on a body diagram.
- 4. The Investigator or designee will assess the treated areas by observations and questioning the subjects as necessary for the signs and symptoms of irritation including pain/burning, pruritus, erythema, edema, and scabbing/crusting.
- 5. The Investigator will question the subject about any concurrent illness or systemic sign or symptom including but not limited to fatigue, loss or change in taste, nausea, vomiting, diarrhea, muscle spasms or cramps, changes in quality or quantity of hair in treated areas and any change in frequency of shaving or haircuts.
- 6. Collect blood samples for routine laboratory analysis (CBC/Diff and serum chemistry) (*Weeks 6 only*).
- 7. If the subject is a woman of childbearing potential, they will take a home pregnancy urine test and disclose the results to the Investigator or designee (*Weeks 2, 8, and 10 only*).
- 8. The Study Coordinator or designee will weigh the previously dispensed study drug tube. The study coordinator or designee will weigh and dispense a new study drug tube from the subject assigned kit if necessary. (*Baseline and Week 6 only*)
- 9. Any missed doses or deviations should be reported.
- 10. The Study Coordinator or designee will remind the subject of the proper technique for application of the study drug. If needed, the subject can apply the study drug at the investigational center during the day under the direction of the Study Coordinator or designee to confirm proper technique.
- 11. Schedule the next study visit.

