6.8.3 Clinical Laboratory Evaluation

Laboratory test results will be summarized with descriptive statistics at Baseline and Week 12. Additionally, shifts from Baseline to Week 12 in laboratory test results based on normal ranges will be summarized with frequency counts and percentages. Individual laboratory test results will be presented in a by-subject listing.

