6.8.4 Other Observations Related to Safety

6.8.4.1 Dermal Safety and Tolerability

The frequency of dermal safety and tolerability assessments including pain/burning, pruritus, erythema, edema, and scabbing/crusting will be summarized by treatment group and visit. All dermal safety and tolerability results will be listed.

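### Local-reaction grades are tabulated as raw frequencies per visit with no within-tumor comparison to Baseline, so the contrast with vehicle can understate irritation on a regimen that heals tumors

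*Protocol*

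**What the plan says.** Local safety and tolerability belongs to the first primary objective (Protocol 5, SAP 3).

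- **What is graded.** Protocol 9.3.1 states that the "identified BCCs will be evaluated separately for these signs and symptoms of application site reactions". Pain/burning, pruritus, erythema, edema and scabbing/crusting are each graded 0-3. The visit procedures (Protocol 9.1.3 and 9.1.4) describe the area more loosely: "The Investigator or designee will assess the treated areas by observations". The Synopsis says "The study drug will be applied topically to the treatment-targeted BCCs and a rim or adjacent skin for 12 weeks". No separate grade for the rim is planned.
- **State of the site before gel.** Protocol 9.2 describes nodular BCC as "A pearly, waxy, semi-translucent nodule sometimes forming a central depression that may or not be ulcerated or crusted". Table 1 in Protocol 5.1 schedules a "2mm Punch or Shave Biopsy" at Screening, Day -42 to 0, with Baseline on Day 1. Inclusion criterion 5 also accepts an earlier biopsy.
- **Baseline grade.** Protocol 9.1.2, step 7, collects the five signs and symptoms; step 11 places the first application after all clinical assessments.
- **Planned summary.** SAP 6.8.4.1 says the frequencies "will be summarized by treatment group and visit. All dermal safety and tolerability results will be listed". Protocol 10.8.1 says the same. Table 14.3.1.2.1 prints None/Mild/Moderate/Severe counts, with Baseline and each later visit as separate blocks.
- **Other safety data.** SAP 6.8.3 plans "shifts from Baseline to Week 12 in laboratory test results based on normal ranges", and SAP 6.8.4.3 plans change from Baseline for vital signs.

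**The concern.** The grades are labelled reactions to the application, but part of what is graded can be tumor or biopsy wound that was there before the first dose. Frequencies per visit cannot tell a site that stayed crusted from one that healed while another became crusted.

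The more serious part is the comparison with vehicle. The ISGTA (Protocol Table 4) counts erythema, scale, erosions and ulceration of the same lesion as signs of tumor. A regimen that clears the tumor can therefore lower its own local-reaction grade. That healing happens after randomization and differs by arm if the drug works, so randomization does not remove it. The trial is meant to inform the dose and regimen for later studies. The regimen most likely to have its irritation understated is the one most likely to be carried forward.

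**Working it through.** The documents give no crusting, healing or irritation rate, and no power or sample-size inputs, so there is no figure to reproduce. All rates below are assumptions.

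**Within one arm.** Take 12 tumors, 5 crusted and 7 clear at Baseline. Four crusts heal and four clear sites become crusted. The later count is 5 - 4 + 4 = 5. The planned table shows 5/12 at both visits; a shift table shows 4 of 7 clear sites worsening.

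**Against vehicle.** Let b be the share of sites crusted at Baseline, hA and hV the share of those that heal on active and on vehicle, and q the share of Baseline-clear sites that the active gel newly crusts. Assume vehicle crusts none.

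- Later crusting on active = b(1 - hA) + (1 - b)q
- Later crusting on vehicle = b(1 - hV)
- Raw difference = (1 - b)q - b(hA - hV)
- Sites that worsened = (1 - b)q on active, 0 on vehicle

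The raw difference falls short of true worsening by b(hA - hV), the extra healing on active.

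With b = 0.5 and q = 0.3:

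| Healing, active / vehicle | Raw crusting, active | Raw crusting, vehicle | Raw difference | Worsened, active / vehicle |
|---|---|---|---|---|
| 80% / 80% | 0.5×0.2 + 0.5×0.3 = 25% | 0.5×0.2 = 10% | +15 points | 15% / 0% |
| 80% / 40% | 25% | 0.5×0.6 = 30% | -5 points | 15% / 0% |

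The result depends on b. Keep q = 0.3 and hA - hV = 0.4:

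| b | Raw difference | Worsened on active |
|---|---|---|
| 0.2 | 0.24 - 0.08 = +16 points | 24% |
| 0.4 | 0.18 - 0.16 = +2 points | 18% |
| 0.5 | 0.15 - 0.20 = -5 points | 15% |
| 0.6 | 0.12 - 0.24 = -12 points | 12% |

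The raw excess vanishes when hA - hV = (1 - b)q/b, which at b = 0.5 and q = 0.3 is 0.15/0.5 = 30 points of extra healing.

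**Chance imbalance at Baseline.** Each active arm has 6 subjects (Protocol 5.1). SAP 6.1 pools vehicle over four cohorts, 4×3 = 12. With one tumor per subject and assumed Baseline crusting p, the SD of the arm difference is sqrt(p(1 - p)(1/6 + 1/12)): 20 points at p = 0.2 and 25 points at p = 0.5. The exact binomial chance that a given arm differs from vehicle by 25 points or more is 30% at p = 0.2 and 41% at p = 0.5. The Baseline block makes such an imbalance visible but does not adjust for it.

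**The case against.** The strongest reply is the vehicle group. Disease crusting and biopsy healing occur in every arm and cancel in expectation. The first row of the healing table shows this: with equal healing the planned table gives 25% against 10%, exactly the 15 points that worsened. A reader might infer from a fall of 50% to 25% on active alone that the plan hides irritation outright. The documents do not support that, because the trial is randomized and the table is by treatment group. This part of the reply stands, and only drug-driven healing survives it.

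A second reply is that the real limit is sample size, which a shift table does not cure. This also stands. Take 40% crusted at Baseline, 80% healing in both arms, and gel crusting 35% of clear or healed sites. Raw crusting is then 40% against 8%, and none-to-any worsening is 21% against 0%. A two-sided Fisher test at 0.05 with 6 against 12 sites detects the raw contrast with probability 25% and the worsening contrast with 11%; with 12 against 24 independent sites the figures are 58% and 47%. The case for shifts is what they measure, not power, and SAP 6.1 plans no formal testing.

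Third, there are safeguards. The Baseline block is printed, and Listing 16.2.7.1.1 gives every grade by tumor and visit. Reactions that need therapy or cause interruption or discontinuation are AEs (Protocol 9.3.1), as is clinically significant worsening of an abnormal assessment (Protocol 9.3.5.9). These help, but a listing is not a planned summary, and milder irritation can fall outside the AE rules.

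Two further readings go too far. A reader might take grading to be confined to the tumor, but the visit text refers to treated areas; the gap is that tumor and rim are not graded apart. A reader might also take every target to have been biopsied within six weeks of Baseline, but inclusion criterion 5 allows a biopsy before Screening, although Screening also schedules one.

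**Conclusion.** The concern holds in a limited form. The plan collects a pre-dose grade on a site that may already be abnormal, then reports local reactions without linking later grades to it. Where active drug heals tumors more than vehicle does, the raw contrast understates irritation by b(hA - hV). In the worked case that is 0.5×0.4 = 20 points, enough to turn a 15-point true excess into a 5-point apparent advantage. At 20% Baseline crusting the same assumptions leave a 16-point raw excess out of 24. With no differential healing there is no bias, only small numbers.

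Size and direction rest on assumed rates, so the documents support saying that irritation can be understated, not that it will be. The effect is on how part of the first primary objective is read; sample size and error rates are untouched. The change should be made because the data are already collected.

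**What to change.** In SAP 6.8.4.1, add by treatment group:

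- For erythema, edema and scabbing/crusting, a per-tumor shift from the Baseline grade at each visit and to the worst post-Baseline grade.
- Counts of tumors, and of subjects, worsening by at least 1 grade, shown also for tumors graded 0 at Baseline, where a new sign cannot be carried over from a pre-dose grade.
- The same tables for pain/burning and pruritus, with a footnote that recall covers 24 hours at Baseline but the time since the last visit afterwards. Worsening in these two compares unequal windows and may be inflated.

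Keep the raw by-visit table and read the two together. While editing, reconcile the footnote of Table 14.3.1.2.1, which calls all local scores subject-reported, with Protocol 9.3.1, where the Investigator grades erythema, edema and scabbing/crusting.

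The cost is a few extra tables with small counts and no new assessments. One limit remains: irritation that replaces an equal or higher Baseline grade is still not detected, and a tumor at grade 3 cannot worsen. Footnote both.
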